- Evaluation of quality of life in CML patients after imatinib discontinuation/resumption.
- Evaluation of progression/resistance in patients who relapse after imatinib discontinuation.

Endpoints:

Primary Endpoint:

- Negative Predicted Rate (NPV) of dPCR, i.e. the capability of the method to predict relapse-free patients.

Secondary Endpoints:

- Rate of dPCR positive relapse-free patients after 3 years follow up.
- Rate of relapse-free patients after 3 years follow up.
- Relapse free time.
- Quality of Life, as measured by EORTC-QLQ-T30 questionnaire.
- Rate of patients progressing or developing resistance after imatinib suspension.

Study Design and Methods:

In this study dPCR analysis will be performed on CML patients under imatinib therapy, with at least 18 months of consecutive negative standard Q-RT-PCR as performed in their own centers. The patients will sign an informed consent form (ICF), will subsequently be tested for dPCR and will stop imatinib. Then they will be monitored with standard Q-RT-PCR to assess the maintenance of the molecular remission. Collection of data will be prospective as each center will collect the data for 36 months. At the end of this period, a peripheral blood sample for dPCR analysis will be obtained from those patients who will still have undetectable BCR/ABL transcripts by Q-RT-PCR to verify CML eradication. Two years follow-up is then planned for patients maintaining CMR. During study, the patients with BCR/ABL transcripts detected by standard Q-RT-PCR will repeat the test not before 2 weeks and not after 2 months; in case of results confirmation and at least one BCR/ABL / BCR value >0.1%, the loss of the molecular remission will be declared and hematologic and bone marrow analyses will be performed. Such patients will immediately resume imatinib treatment at the same dosage used before interruption; progression of the disease will be evaluated as evolution to AP or BP and resistance to treatment will be defined as lack of complete hematological response at 3 months or of complete cytogenetic response at 6 months after resuming imatinib.

Patient's life quality during imatinib discontinuation/resumption will be evaluated through a Quality of Life (QoL) questionnaire until the end of this study (for patients maintaining molecular remission at baseline and at months 1, 6, 12, 24, 36, for relapsing patient at months 1, 6, 12 after imatinib resumption).

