The eligible patients will be entered between September 2011 and August 2012. Approximately 14 Centers will be involved in the study, including 5 international Centers.

Sample size

Sample size will be calculated so to provide with 80% power the alternative hypothesis that the Negative Predicted Value (NPV) of dPCR (i.e. the capability of the method to predict relapse-free patients) will exceed the one of traditional Q-RT-PCR, by more than 1.5.

$$H_0(N): rNPV \leq \delta$$

$$H_1(N): rNPV > \delta$$

where rNPV is the ratio of the Predicted Negative Values by the two tests respectively.

Promoter: University Milano-Bicocca

Product: Imatinib

With reference to the table below:

$$rNPV = \frac{NPV_{dPCR}}{NPV_{Q-RT-PCR}} = \frac{(n_{3+} n_4) / (n_{3+} n_4 + n_{6+} n_8)}{(n_{2+} n_4) / (n_{2+} n_4 + n_{6+} n_8)}$$

	Relapse Free 3 years since discontinuation			Relapsed within 3 years since discontinuation		
	Q-RT-PCR at entry			Q-RT-PCR at entry		
dPCR at entry	Positive	Negative	Total	Positive	Negative	Total
Positive	n ₁	n ₂	n ₁₊ n ₂	n ₅	n ₆	n ₅₊ n ₆
Negative	n ₃	n ₄	n ₃₊ n ₄	n ₇	n ₈	n ₇₊ n ₈
	n ₁₊ n ₃	n ₂₊ n ₄	N _{R-}	n ₅₊ n ₇	n ₆₊ n ₈	N _{R+}

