The studies estimating the relapse rate of patients after discontinuation of imatinib are still limited in number, based on a relatively low number of patients, heterogeneous by time on treatment, observation time accrued after discontinuation and therapy preceding imatinib (39, 40, 41). According to the preliminary results of the STIM study (40) that included patients in CMR for at least 24 months, 42 out of 69 patients followed for 13-30 months (median 24 months) since imatinib discontinuation relapsed. Thirty-nine percent (95% CI 28-51%) of patients were still negative at Q-RT-PCR performed at repeated occasions after discontinuation. Due to the lack of robust estimates, the sample size has been calculated assuming that $NPV_{Q-RT-PCR}$ equals to the lower limit of the 95% CI of the relapse free rate reported above i.e. 28%. If true rate of $NPV_{Q-RT-PCR}$ is higher the sample will provide the test with more power. Also, according to a pilot experience conducted within ILTE protocol, only 1/3 of patients negative by Q-RT-PCR are also negative by dPCR. Finally, n₃ and n₇ were assumed to be 0 because, being the dPCR method more sensitive than Q-RT-PCR, it is highly unlikely that the former turns to be negative when actually the latter is positive. With $\alpha=0.05$, $\beta=0.20$, $\delta=\gamma=1.5$ under the alternative hypothesis and the above assumptions the sample size required calculated according to reference (42) is 98 patients.

Definition of Analyzed Study Populations

All enrolled patients will be evaluated. Patients who withdraw or die before 36 months from the day 1 of the study will be considered as not evaluable.

Analyses

The data will be analyzed by Milano International Oncology or designee. rNPV will be calculated as the ratio of the Predicted Negative Values by the two tests respectively. If the lower 95% confidence limit will be greater than 1.5 one would conclude that the new method is more effective in predicting negative value as compared to the traditional one.

Progression free survival computed as the day since enrolment to the day of relapse or death will be analyzed by Kaplan-Maier method. The sensitivity and specificity of dPCR to predict molecular relapse will be assessed, as well as the overall and progression free survival of patients.

Promoter: University Milano-Bicocca

Product: Imatinib

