The following variables will be monitored: dPCR results, number and time of relapses (molecular, cytogenetic or hematological), presence of progression AP/BP at relapse, best response obtained after imatinib reintroduction. Quality of life will be evaluated before and after imatinib suspension and after eventual imatinib resumption.

Interim Analyses:

Interim analyses will be conducted 1, 2 and 3 years after the day of last patient enrollment.

Subject Selection:

Subject inclusion criteria:

Subjects must meet all of the following inclusion criteria to be eligible for enrollment into the study:

1. Signed and dated IRB/IEC-approved Informed Consent.
2. Age > 18 years.
3. Male or female patients with CML diagnosed in chronic phase and who have been treated for more than 2 consecutive years with Imatinib therapy.
4. Achievement of CMR (as defined by their own center) sustained for at least 18 months with imatinib treatment.
5. A minimum of 3 CMR determined by Q-RT-PCR analysis to support disease status, with the last one performed within 3 calendar months prior to enrollment date.
6. Willingness and ability to comply with scheduled visits, laboratory tests and other study procedures.

Subject Exclusion Criteria:

The presence of any of the following will exclude a subject from study enrollment:

1. Allogenic hematopoietic stem cell transplantation.
2. Known active infections, including human immunodeficiency virus (HIV) positivity.
3. Current enrollment in another clinical trial.
4. Other severe acute or chronic medical or psychiatric condition or laboratory abnormality that may increase the risk associated with study participation or study drug administration or may interfere with the interpretation of study results and, in the judgment of the Investigator, would make the patient inappropriate for entry into this study.

Trial Product

In case of loss of molecular remission the patients will resume imatinib treatment at the same dosage used before interruption. In case of treatment resumption, imatinib will be administered as home-based treatment. Imatinib is marketed and used for the treatment of CML so it do not represent an additional cost for the study and will be supplied by the National Health Service. Imatinib is commercially available in rigid capsules of 50 mg. Imatinib is to be stored at room temperature not exceeding + 30°C and in the original packaging, out of the reach and sight of children.

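### The analysis labelled progression-free survival counts relapse as its event and starts at enrolment, so as written it is relapse-free survival on a clock that differs from the discontinuation clock in the Sample size table

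*Protocol*

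**What the plan says.** All references are to the protocol.

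- **Analyses**, definition: "Progression free survival computed as the day since enrolment to the day of relapse or death will be analyzed by Kaplan-Maier method". The next sentence of that section promises overall and progression-free survival again, with no second definition.
- **Study Design and Methods**, relapse: "in case of results confirmation and at least one BCR/ABL / BCR value >0.1%, the loss of the molecular remission will be declared".
- **Study Design and Methods**, progression: "progression of the disease will be evaluated as evolution to AP or BP".
- **Analyses**, list of monitored variables: relapse is one item, "number and time of relapses (molecular, cytogenetic or hematological", and progression is another, "presence of progression AP/BP at relapse".
- **Endpoints**: relapse-free time is a secondary endpoint, with no event or time zero given. A separate secondary endpoint reads "Rate of patients progressing or developing resistance after imatinib suspension". Progression-free survival is not in the list.
- **Sample size**, table heading: "Relapse Free 3 years since discontinuation".
- **Study Design and Methods**, order of steps: "The patients will sign an informed consent form (ICF), will subsequently be tested for dPCR and will stop imatinib". No interval is stated.
- **Definition of Analyzed Study Populations**: the 36-month evaluability rule counts from study day 1, which is not defined.

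**The concern.** There are two faults of unequal weight.

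The first is the event. The protocol gives progression a specific meaning, then uses the word in a survival endpoint whose event is something else. The Study Rationale describes relapse as reversible once imatinib is resumed. In a trial of stopping an effective drug, a reader of a progression-free survival curve will take each drop as disease evolution or death. Most drops are likely to be molecular relapses, since the protocol's own source study saw 42 relapses in 69 patients. The risk of stopping would then be misread from the label.

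The second is time zero. Patients cannot relapse off drug before they stop the drug. If stopping comes later than enrolment, the days between are counted as relapse-free time although they were spent on treatment.

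**Working it through.** **1. Event: the definitions side by side**

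| Term | Where | Event |
|---|---|---|
| Relapse (loss of molecular remission) | Study Design and Methods | Confirmed positive Q-RT-PCR with at least one value above 0.1% |
| Progression | Study Design and Methods | Evolution to AP or BP |
| Progression-free survival | Analyses | Relapse or death |
| Relapse-free time | Endpoints | Not stated |
| Rate of progression or resistance | Endpoints | Progression or resistance, as a proportion |

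Take a patient with a confirmed molecular relapse who never reaches AP or BP. Under the Study Design and Methods definition this patient has not progressed. Under the Analyses definition the patient has a progression-free survival event on the day of relapse. Both cannot hold. The quantity that Analyses describes is relapse-free survival. The time-to-event endpoint that is listed has no analysis under its own name, and the one that is analysed is not listed.

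**2. Clock: the starting points side by side**

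| Quantity | Time zero |
|---|---|
| Kaplan-Meier analysis (Analyses) | Enrolment |
| 3-year relapse status (Sample size table) | Discontinuation |
| Rate of progression or resistance (Endpoints) | After suspension |
| 36-month evaluability (Definition of Analyzed Study Populations) | Study day 1, undefined |

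**3. Illustration of the clock effect**

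The gap g between enrolment and stopping is not in the document, so 0, 1 and 3 months are assumptions. Two more assumptions are needed: relapse is exponential from the stop date, and 39% are relapse-free at 24 months. The 39% is the source-study figure in Sample size, where follow-up was 13–30 months with a median of 24.

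- Rate: λ = −ln(0.39)/24 = 0.0392 per month.
- Clock at discontinuation: S(t) = exp(−λt).
- Clock at enrolment, with no relapse during the gap: S(t) = exp(−λ(t − g)) for t > g.

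| Gap g | Month 6 | Month 36 | Median (months) |
|---|---|---|---|
| 0 | 79.0% | 24.4% | 17.7 |
| 1 month | 82.2% | 25.3% | 18.7 |
| 3 months | 88.9% | 27.4% | 20.7 |

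The median moves by exactly the gap. The distortion is larger early, where the curve is steeper, and small at 36 months. With g = 0 there is none.

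**4. Does the primary design depend on this?**

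The plan's one design figure is 98 patients. Inputs from Sample size: NPV of Q-RT-PCR 0.28; ratio 1.5, so NPV of dPCR = 0.28 × 1.5 = 0.42; fraction dPCR-negative f = 1/3; n₃ = n₇ = 0; α = 0.05; power 80%. I take α as one-sided and the null ratio as 1.

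- V = (1 − 0.42)/(0.42 × 1/3) + (1 − 0.28)/0.28 − 2(1 − 0.42)/0.28 = 4.143 + 2.571 − 4.143 = 2.571.
- N = (1.645 + 0.842)² × 2.571/(ln 1.5)² = 96.7, so 97. With f rounded to 0.33 it is 98.3, so 99.

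The stated 98 is matched to within rounding of f. With two-sided α the result is 123, which does not match. No term in the calculation involves progression-free survival or its clock, so the figure stands whichever way this point is settled.

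**The case against.** The best defence is that this is a naming fault in an analysis that is not even a listed endpoint, and that Analyses prints the event next to the label, so a careful reader can see what is measured. That is fair on severity. It does not remove the contradiction, because labels travel into reports without their definitions.

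Four stronger readings are tempting, and the protocol does not support them.

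- **That the enrolment clock misclassifies the primary endpoint.** A reader might infer that patients with under 36 months off drug are counted as relapse-free at 3 years. The Sample size table already counts from discontinuation, and the Kaplan-Meier sentence does not feed it. The only opening is the undefined day 1 in the evaluability rule, which may itself be the stop date.
- **That the mislabelled curve would stand at 28–39% at 36 months.** The 39% is a crude 27/69 at 13–30 months of follow-up, and 28% is its lower confidence limit. Neither is a 36-month estimate; the exponential assumption above gives 24.4%. The source figure describes patients still PCR-negative, which is not this protocol's relapse definition, and it leaves out deaths.
- **That progression goes unreported.** It has its own objective and its own rate endpoint. What is absent is a time-to-AP/BP analysis under the progression-free label.
- **That every date needed is already recorded.** The monitored variables include the time of relapse and AP/BP at relapse. They do not name a stop date or a date of AP/BP after relapse.

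It is also true that no section sets discontinuation as time zero for this particular analysis, so the clock point is an inconsistency between related quantities and not a flat contradiction.

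**Conclusion.** The point holds for the event, with high confidence and from the text alone: the analysis called progression-free survival is relapse-free survival, contrary to the protocol's own meaning of progression. This cannot be left to a statistical analysis plan, because the protocol fixes both event and time zero. A plan that followed it would inherit the fault, and one that departed from it would contradict the protocol.

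The clock point holds as a secondary matter. Its direction is known, since any gap lengthens apparent relapse-free time. Its size is not: it is zero if stopping coincides with enrolment. The illustrated shifts at 36 months, 0.9 percentage points for one month and 3.0 for three, rest on assumed gaps and exponential relapse.

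The consequence is a mislabelled secondary outcome that should be corrected. The primary comparison of predictive values and the sample size of 98 do not change.

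**What to change.** 1. In Analyses, rename the analysis relapse-free survival, state that it is the analysis of the listed endpoint of relapse-free time, and run it from the imatinib stop date to declared relapse or death.
2. If progression-free survival is also to be reported, define its event as AP/BP or death, from the same time zero. Otherwise remove the term and leave the rate of progression or resistance as the progression endpoint.
3. Define study day 1 as the imatinib stop date, so that the 36-month evaluability rule matches the Sample size table.

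The cost is protocol wording, plus a check that the case report form captures the stop date and, if item 2 is adopted, the date of AP/BP, including evolution after relapse. No extra patients or visits follow from these changes.
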